7.4 Investigator's Regulatory Binder

Investigators shall maintain a Regulatory Binder provided by the Sponsor.

7.5 Record Retention Period

Investigators shall maintain all study related documentation for a period of two years following completion of the study.

8 STUDY ETHICS AND CONDUCT

8.1 Role of the Sponsor

As the study sponsor of this clinical trial, AngioDynamics has the overall responsibility for the conduct of the study, including assurance that the study meets the requirements of the appropriate regulatory bodies. In this study, the sponsor will have certain direct responsibilities and may delegate other responsibilities to the CRO.

8.2 Ethical Conduct of the Study

The investigator agrees that the study will be conducted according to the applicable FDA regulations (21 CFR). The investigator will conduct all aspects of this study in accordance with all national, state, and local laws or regulations.

8.3 Institutional Review Board (IRB)

Federal regulations, ISO 14155 and 21 CFR 56 require that approval be obtained from an IRB prior to participation of subjects in research studies. Prior to subject enrollment, a signed copy of the IRB approval letter must be submitted to AngioDynamics. In addition, the protocol, informed consent, advertisements to be used for subject recruitment, and any other written information regarding this study to be provided to the subject and/or the subject's legal authorized representative, must be approved by the IRB. Documentation of all IRB approvals will be maintained by the site and will be available for review by the sponsor or its designee.

All IRB approvals should be signed by the IRB chairperson or designee and must identify the IRB by name and address, the clinical protocol by title and/or protocol number, and the date approval was granted. The Investigator is responsible for submitting and obtaining initial and continuing review of the trial at intervals not exceeding 1 year or as otherwise directed by the IRB. The investigator must supply the sponsor or its designee written documentation of continued review of the study.

8.4 Confidentiality

A Subject Identification Log shall link the data collected during the study to source documents such as hospital records and medical charts. The Subject Identification Log shall be kept in a secure location with restricted access.

All information collected during the course of this study will be kept confidential, except that sponsor's representatives, local IRB and FDA will have access to this information.

The sponsor's representatives and/or FDA will have access to relevant medical charts or hospital files for purposes of source data verification. A HIPAA waiver shall be obtained as part of the Informed Consent Form from the IRB giving access to the source data for this purpose.

No information which could identify a subject will be used in reports or publications.

Subjects will remain anonymous for data analysis. Should the study require a future review of source documentation collected after official close-out (data collected after the 12-month follow-up visit), it will be necessary to obtain an additional informed consent and waiver of authorization for access to medical records from the IRB.

8.5 Subject Compliance

Subjects' participation in the study will terminate when they either complete the 12-month follow-up visit or discontinue participating in the study prior to completion. The reason for the subject's termination from the study will be documented on the Termination CRF. Upon study completion or termination, each subject will be instructed to visit his referring physician for evaluation and monitoring and/or treatment following the best practice guidelines for intermediate risk subjects.

Subjects may voluntarily withdraw from the study at any time, but a physician cannot arbitrarily remove a subject from the investigation. The reason for all subject withdrawals should be documented. If a subject is withdrawn from the study, every effort will be made to continue to follow the subject for safety, including the use of phone calls (up to three) and couriered mail, to obtain safety follow-up information.

Subjects will be required to meet the follow-up visit schedule outlined in *Table 4-4*.

8.6 Follow-Up

Subjects requiring follow-up will be reminded of their follow-up visits via telephone calls and a certified letter, if necessary. The investigator will keep a record of follow-up attempts in the Subject Follow-Up Log. A subject will be deemed lost-to-follow-up after the inability to obtain a response from the subject or legal representative on three separate occasions separated by at least one day. These contacts may be telephone calls or emails to the subject or legal guardian, or the primary care provider if the subject is unable to be contacted. However, at least one effort using a certified letter should be attempted at the last known address.

8.7 Medical Risk Analysis

Because the NanoKnife System is investigational within the prostate there may be potential risks and side effects that are unknown at this time. A clinical risk analysis has been prepared which describes the hazards associated with the use of the device and the associated clinical risks associated with the procedure (e.g., general anesthesia) along with the mitigations available to reduce this hazard. Potential risks associated with the use of the NanoKnife System include, but are not limited to, the risk outlined in *Table 8-1*.

Table 8-1: Potential Hazards

Hazard	Potential Effect(s)	Early Recognition	Mitigation
General anesthesia (procedural)	Aspiration-infection Pulmonary compromise-ARDS Urinary retention, suprapubic catheterization Paralysis Coma Death	Periodic assessment of airway patency, respiratory rate, and oxygen saturation. Routine monitoring of vital signs	Supervision by trained anesthesiologist Intra-operative monitoring Pre-op history and physical exam
Muscle Blockade (procedural)	Extended anesthesia (too much blockade) Insufficient anesthesia—pain Toxicity (If the organ that metabolizes the muscle block has compromised function)	Physical assessment and pharmacological management per ASA Standards	Pre-op history and physical exam Selection of appropriate agents. Patient management by Anesthesiologist.
Cardiac Arrhythmia (both procedural and device, unlikely from device due to distance)	Acute decrease in BP Fibrillation Cardioversion Death	The Anesthesiologist will be monitoring the patient continuously during procedure.	Anesthesia monitoring History and physical exam Availability of treatment drugs and cardioversion equipment; ECG monitoring and procedure pacing
Multiple Prostate Biopsies (procedural)	Bleeding Infection Hematoma Pain	Needle placement is performed using continuous image guidance.	Biopsy technique and physician training
IRE electrode needles placed in or through sensitive structures. (Foreseeable misuse)	Sharp trauma / perforation of structures. (Blood vessels, nerves, urethra, bowel, bladder). Bleeding Infection. Pain	Probe placement is performed using continuous image guidance. Patients will be monitored for hemodynamic instability	Physician training; product labeling
Insufficient Muscle Blockade (procedural)	Muscle strains or damage. Electrodes moved out of position. Disruption of drapes (contamination of sterile field) Trauma (to patient and medical staff) from flailing limbs.	Patient assessment by Anesthesiologist	Choice of agent and dose Subject observation Physician training

Hazard	Potential Effect(s)	Early Recognition	Mitigation
Vascular Dissection (device)	Nerve damage Hematoma Surgical intervention Transfusion Death	Probe placement is performed using continuous image guidance. Patients will be monitored for hemodynamic instability.	Proper positioning and imaging guidance Physician training
Perforation (device)	Infection Fever Sepsis Coagulopathy Death	Monitoring of patient condition for signs of sepsis, hemodynamic instability	Proper positioning and imaging guidance Physician training
Hemorrhage (device)	Hematoma Surgical intervention Transfusion Increased recovery time Death	Patients will be monitored for hemodynamic instability	Proper positioning and imaging guidance Physician training Observation of subject during procedure
Lack of Sterile Technique/Breach of Sterile Field (procedural)	Infection Abscess Fever Sepsis Coagulopathy Death	Monitoring of patient vital signs, monitoring for signs of sepsis.	Inspection of device packaging prior to use Sterilization and package integrity validation
ECG (EKG) Disruption after pulsing (2-3 sec)	Delayed intervention (can substitute arterial pulse until ECG returns)	The Anesthesiologist will be monitoring the patient continuously during procedure. The ECG monitoring device will alarm.	Validation of ECG pacing and interface if used
Nerve Damage (device)	Erectile Dysfunction	Probe placement is performed using continuous image guidance.	Nerve sparing nature of IRE; placement of needles and conduct of procedure using appropriate imaging observation
Acute or Sub-acute Vascular Damage (device)	Infarction /necrosis of non-targeted prostate tissues	Probe placement is performed using continuous image guidance. The NanoKnife generator provides precise control of probe voltage and duration, as well as automatic current limits and reporting of pulse currents.	Pre-procedure planning Physician training Use of imaging for guidance
Injury to Prostatic Urethra or External Sphincter (device)	Urinary incontinence Impotence Surgical repair Lifestyle changes	Probe placement is performed using continuous image guidance.	Pre-procedure planning Physician training Use of imaging for guidance

Hazard	Potential Effect(s)	Early Recognition	Mitigation
Urethro-rectal Fistula (procedural or device)	Pain Fever Abscess formation Infection, sepsis Surgical repair	Probe placement is performed using continuous image guidance. The NanoKnife generator provides precise control of probe voltage and duration, as well as automatic current limits and reporting of pulse currents.	Pre-procedure planning Physician training Use of imaging for guidance
Rectal Tear/ Perforation (from TRUS guided biopsy or Endorectal MRI coil) (procedural)	Pain Fever Abscess formation Infection, sepsis Surgical repair	Monitoring of patient condition for signs of sepsis.	Pre-procedure planning Physician training Use of imaging for guidance
Postoperative Hemorrhage (device)	Blood transfusion Pain Hematoma Medical/surgical intervention Death	Probe placement is performed using continuous image guidance. Patients will be monitored for hemodynamic instability.	Pre-procedure planning Physician training Use of imaging for guidance Avoidance of unnecessary needle insertion

Other accepted focal treatments for prostate neoplasia, such as percutaneous prostate cryoablation, have limitations such as variable damage at the lesion margins, injury to adjacent structures such as the rectum, urethra and neurovascular bundle, and long procedure times. These characteristics have limited the widespread acceptance of this modality despite certain demonstrated advantages over the more traditional treatments of radiation and radical prostatectomy.

The NanoKnife System utilizes irreversible electroporation (IRE), a non-thermal ablation modality that uses short pulses of DC electric current to create irreversible pores in the cell membrane, thus causing cell death. This method has been shown to have significant advantages in ablating hepatic tissue, such as rapid lesion creation, rapid lesion resolution, sparing of structures such as vessels and bile ducts, and uniform destruction throughout the IRE lesion. It is theorized that these advantages will also apply to use in the prostate.

8.8 Protocol Deviations

The investigator will not knowingly commit a major protocol deviation without prior written approval from the sponsor except in medical emergencies or in unforeseen, isolated instances where minor changes are made that will not increase the subject's risk or affect the validity of the trial. In medical emergencies, prior approval for protocol deviations will not be required, but the sponsor must be notified within two working days of the incident. Periodic monitoring of protocol compliance will be performed for each site. The sponsor has the right to suspend enrollment at sites deemed to have excessive protocol compliance issues.

All deviations related to study inclusion or exclusion criteria, conduct of the trial, subject management or subject assessment must be appropriately documented and reported. Other protocol deviations to

be considered include non-adherence to the protocol that results in a significant additional risk to the subject, or non-adherence to FDA regulations and/or ISO 14155.

The investigator must document and explain any protocol deviation in the subject's source documentation. The IRB should be notified of all protocol deviations in a timely manner. Protocol deviations should be reported to the IRB periodically, according to their requirements. Deviations will also be documented by the monitor during site visits and those observations will be reviewed with the investigator.

If the investigator believes that any exception to the protocol is justified for an individual subject or if the investigator has a question concerning a subject who may not meet an eligibility criterion, they should contact the sponsor's medical monitor. The sponsor will evaluate circumstances where the investigator deviates from the study protocol and will retain the right to remove either the investigator or the investigational site from the study.

The following deviations will be considered major deviations for the purposes of defining the Per Protocol analysis population:

- Subjects who are not consented for the trial
- Subjects for whom the intended ablation is not delivered
- Subjects who are not intermediate risk, defined as Gleason score 3+4 or 4+3, PSA ≤ 15 ng/mL or PSA density < 0.15 ng/mL² if PSA is > 15 ng/mL, and \leq clinical stage T2c
- Subjects who miss three consecutive follow-up visits
- Subjects who have had prior or current prostate cancer therapies:
 - Biologic therapy for prostate cancer
 - Chemotherapy for prostate cancer
 - Hormonal therapy for prostate cancer within three months of procedure
 - Radiotherapy for prostate cancer
 - Surgery for prostate cancer

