4.3.1 Inclusion Criteria

A subject is required to fulfill all of the following criteria to be included in the study:

1. Is greater than 50 years of age

2. Has at least a 10-year life expectancy
3. Has histologically confirmed organ-confined prostate cancer, clinical stage \leq T2c
4. Has a PSA \leq 15 ng/mL or PSA density < 0.15 ng/mL² if PSA is > 15 ng/mL
5. Has Gleason score 3+4 or 4+3
6. Has no evidence of extraprostatic extension by mpMRI
7. Has no evidence of seminal vesicle invasion by mpMRI, and if suspected, confirmed by biopsy
8. Physician is able to visualize prostate gland adequately on transrectal ultrasound imaging during qualifying biopsy
9. Has a transperineal or transrectal targeted prostate biopsy of lesion, plus 10-14 core systematic biopsy to include adequate sampling of the peripheral zone correlating with an intermediate risk lesion³ in the area of the MR-visible lesion
10. A visible lesion on mpMRI that is accessible to Irreversible Electroporation (IRE) treatment (Note: prostate cancer detected via systematic standard biopsy outside of the adjacent sextant location of the MRI visible lesion will meet entry criterion provided the positive core is Gleason 6; has fewer than 3 prostate biopsy fragments/cores positive and $\leq 50\%$ cancer in each of those fragments/cores on standard biopsy)
11. Is willing and able to sign a written informed consent and in the judgment of the physician, the study is in the best interest of the subject
12. Understands and accepts the obligation and is logistically able to present for all scheduled follow-up visits

4.3.2 *Exclusion Criteria*

A subject will be excluded from the study if they meet any of the following criteria:

1. Has known hypersensitivity to pancuronium bromide, atracurium or cisatracurium
2. Is unfit for anesthesia or has a contraindication for agents listed for paralysis
3. Has an active urinary tract infection (UTI)
4. Has a history of bladder neck contracture
5. Is interested in future fertility
6. Has a history (within 3 years) of inflammatory bowel disease
7. Has a concurrent major debilitating illness
8. Had active treatment for a malignancy within 3 years, including malignant melanoma, except for prostate cancer or other types of skin cancer
9. Has any active implanted electronic device (e.g., pacemaker)
10. Is unable or unwilling to catheterize
11. Has had any prior or current prostate cancer therapy, including:
 - a) Biologic therapy for prostate cancer

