If the subject is re-biopsied, and there is a positive in-field core, this subject will be considered a failure for the primary efficacy endpoint (see Section 6.7). If the subject and the positive lesion still meet all of the inclusion criteria and none of the exclusion criteria⁴ (i.e., the lesion is an intermediate-risk lesion of Gleason 3+4 or 4+3 and all other criteria are met), the subject can be re-treated with the NanoKnife System and will continue to be followed up for the duration of the study for secondary efficacy endpoints and safety. If the subject and their treating physician decide on re-treatment with something other than the NanoKnife System, or if they no longer meet the inclusion/exclusion criteria for the study (i.e., they have a Gleason \geq 4+4 lesion and require whole-gland treatment), their post-re-treatment data will be excluded from the analysis.

Positive Early Out-of-Field Biopsy:

If the subject is re-biopsied, and there is a positive out-of-field core, this will not be considered a failure for the primary efficacy endpoint. If the subject and the new positive lesion still meet all of the inclusion criteria and none of the exclusion criteria⁵ (i.e., the new lesion is an intermediate-risk lesion of Gleason 3+4 or 4+3 and all other criteria are met), the subject can be re-treated for the new lesion with the NanoKnife System as part of the study. If the subject and their treating physician decide on re-treatment with something other than the NanoKnife System, or if they no longer meet the inclusion/exclusion criteria for the study (i.e., the new lesion is Gleason \geq 4+4 and the subject requires whole-gland treatment), they will exit the study though will continue to be followed for safety. These subjects who were re-treated with something other than the NanoKnife System for an out-of-field lesion prior to 12 months will have their post-re-treatment data excluded from the analysis.

Negative Early Biopsy:

If the subject is re-biopsied and there are no positive findings, they will continue in the study as planned, completing follow-up visits and the scheduled mpMRI and biopsy at 12 months.

If a subject is re-treated, regardless of the re-treatment selected, they should be followed up by the treating physician or their primary physician for routine urological care after the completion of the study.

Additional 'For Cause' Tests:

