'For cause' additional tests such as ultrasound, mpMRI, CT scan, bone scan or PET/CT scan will be permissible. Specifically, an mpMRI at the 3-10 day visit is permitted if clinically indicated (i.e., if the patient is experiencing unexpected adverse events following treatment). 'For cause' biopsy is also permitted, if there is a clinical indication for this e.g., significant rise in PSA 9 – 12 months post-ablation.

Post-Treatment mpMRI:

3-month mpMRI: This will be used to verify that the treatment has been delivered appropriately according to the plan with all areas planned for coverage ablated, and to assess progression as well

⁴ Note: Exclusion criterion #11 for prior or current prostate cancer therapies does not apply.

⁵ Note: Exclusion criterion #11 for prior or current prostate cancer therapies does not apply.

as determining whether appropriate energy has been delivered. This will be performed at the 3-month visit to evaluate the extent and volume of necrosis of the prostate. PI-RADS version 2.1 guidelines and reporting will be utilized.

12-month mpMRI: This will follow the same protocol as the pre-treatment mpMRI during initial screening visit and the post-treatment mpMRI, and reported in the same manner.

See **Appendix A - Standard Operating Procedure: 1. mpMRI Protocol.**

Concomitant Medications and Therapies:

Concomitant medications and therapies will be assessed and recorded during each follow-up visit. These include:

- Urethral dilatation, cystoscopy, bladder neck incision (BNI), and transurethral resection of the prostate (TURP)
- Androgen suppression in any form, radiation therapy to the prostate in any form, focal/whole-gland cryotherapy, focal/whole-gland HIFU or radical prostatectomy
- Alpha blockade, 5 alpha-reductase inhibitors, anti-muscarinic medication
- Treatment-related antibiotics or pain medications

After the completion of 12-month follow-up, subjects will be referred to standard of care clinical follow up. AngioDynamics will be allowed to access EMR and similar medical records outside of the study through five years of follow up in order to assess long-term rate of progression, the need for re-intervention, and adverse events.

Table 4-4. Schedule of Subject Evaluations

Study Assessment	Visit 1	Visit 2	Visit 3	Post-Procedure ¹⁰	Visit 4	Visit 5	Visit 6	Visit 7	Visit 8

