12.1 Subject Disposition

The number and percentage of subjects screened and included in each analysis set will be presented, together with the number and percentage of subjects who withdrew from the study prematurely and a

breakdown of the corresponding reasons for withdrawal. A tabulation of the number and percentage of subjects enrolled at each center will be presented.

If a subject undergoes re-treatment, one re-treatment with IRE for the same lesion will allow the subject to continue in the study. However, if there is more than one re-treatment with IRE on the same lesion or at least one re-treatment with a type of treatment other than IRE, then the subject will exit the study (data until the moment of re-treatment will be used for analysis) and will only be followed up for safety purposes.

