12.7.10 Sensitivity Analyses

All efficacy analysis will be repeated for the PP population. Additionally, a sensitivity analysis in the ITT population will be performed for the primary efficacy endpoint by only including subjects with biopsy data available at 12-months or who has a positive in-field biopsy prior to 12-months (i.e., without performing missing data imputation for subjects with missing biopsy information post-ablation).

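### Read literally, the missed-visit rule in protocol 8.8 drops some known early in-field failures from the Per Protocol set, which can only raise the supportive success rate

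*Combined protocol and SAP*

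**What the plan says.** Protocol 8.8 gives the deviations that count as major for defining PP. They include "Subjects who miss three consecutive follow-up visits". The item carries no exception and does not say whether a visit falling after study exit is missed.

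The related rules are these:

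- **Early failure.** Under protocol 4.6.16, a PI-RADS 3 or higher lesion on the 3-month mpMRI triggers an early biopsy. If a core is positive in-field, "this subject will be considered a failure for the primary efficacy endpoint". Protocol 6.7 and SAP 12.7.1 repeat this.
- **Exit.** SAP 12.1 says that if there is "at least one re-treatment with a type of treatment other than IRE, then the subject will exit the study". Data up to re-treatment are analysed, and later follow-up is for safety only.
- **Visits.** Protocol Table 4-3 and SAP Table 3 schedule months 1, 3, 6, 9 and 12 after the post-procedure contact.
- **Role of PP.** PP is supportive and ITT is primary (protocol 6.3, SAP 9.3). SAP 12.7.10 states: "All efficacy analysis will be repeated for the PP population".
- **Who applies the rule.** SAP 12.5 uses a separate deviation guidance to decide PP exclusions. It allows the criteria to be adjusted during ongoing review and finalised as late as just before database lock. SAP 6.0 notes that the study has no blinding.

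Protocol 8.8 also lists "Subjects who have had prior or current prostate cancer therapies", with five sub-items, one of them "Hormonal therapy for prostate cancer within three months of procedure". Exclusion criterion 11 in protocol 4.3.2 has the same five sub-items under the lead-in "Has had any prior or current prostate cancer therapy, including".

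**The concern.** A missed-visit criterion is normally there to remove poor compliers whose outcome is uncertain. Here it can also remove men whose outcome is known, and known to be bad, because the plan itself sends them out of the study. Membership of PP would then depend on the endpoint.

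What is at stake is the value of PP as a check on ITT. A supportive analysis is informative only if it is free to disagree. One that sheds device failures is biased towards agreeing with ITT or looking better. The open wording also leaves someone to decide, in an unblinded study and possibly with the biopsy result in hand, whether a post-exit visit was missed.

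**Working it through.** **1. Which men the rule catches.** Take a man whose 3-month mpMRI triggers a biopsy, whose in-field core is positive, and who has non-NanoKnife treatment.

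| Exit | Scheduled visits not attended | Three in a row? |
|---|---|---|
| After month 3, before month 6 | 6, 9, 12 | Yes |
| After month 6, before month 9 | 9, 12 | No |
| After month 9 | 12 | No |

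Only exits before the 6-month visit are caught. Nominally that leaves 180 − 90 = 90 days for biopsy, pathology and re-treatment. With the ±14-day windows the range is 166 − 104 = 62 to 194 − 76 = 118 days. The route is feasible but not universal. A man re-treated once with NanoKnife for the same lesion stays in the study and is not caught.

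**2. The plan's own figures.** The documents state no PP size or rate, so there is no PP figure to reproduce. The sample size matters for step 4 because it shows which significance level was used. With p0 = 0.52, p1 = 0.69 and 80% power,

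n = [(z_α √(p0 q0) + z_β √(p1 q1)) / (p1 − p0)]²

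- One-sided 5%: [(1.645 × 0.4996 + 0.842 × 0.4625) / 0.17]² = 50.75, so 51, as stated in protocol 6.2.
- Two-sided 5%, the general rule in SAP 12.0: 64.8, so 65.

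**3. Effect on the PP rate.** With x negatives among N men and k known failures dropped (no other exclusions),

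PP rate = x / (N − k), and the rise over ITT = xk / [N(N − k)], which is positive for any k > 0.

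N = 118 is the planned number. x = 81 comes from 0.69 × 118 = 81.4. The documents do not give k; 4, 6 and 12 (3% to 10% of 118) are assumptions.

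| k | PP rate | Rise (points) | Exact 95% lower limit |
|---|---|---|---|
| 0 | 81/118 = 68.6% | – | 59.5% |
| 4 | 81/114 = 71.1% | 2.4 | 61.8% |
| 6 | 81/112 = 72.3% | 3.7 | 63.1% |
| 12 | 81/106 = 76.4% | 7.8 | 67.2% |

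k = 12 is an upper illustration: it would be 12 of the 118 − 81 = 37 failures.

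**4. Could it change the reading against 0.52?** Not at 81/118, where ITT already clears the goal. Not at 61/118 (51.7%) either: even with k = 12, 61/106 = 57.5% has a two-sided 95% lower limit of 47.6%. Closer to the boundary it can:

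- 72/118 = 61.0% has a two-sided 95% lower limit of 51.6% and misses 52%. With k = 6, 72/112 = 64.3% has a lower limit of 54.7% and passes.
- With the one-sided 5% level that reproduces n = 51, ITT at 72/118 already passes (lower limit 53.1%, exact p = 0.030), so nothing flips there.

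Using the same Clopper-Pearson limits for every x with k = 6, ITT misses and PP passes only at x = 70 to 72 (two-sided 5%) or x = 68 to 70 (one-sided 5%). That is three counts either way.

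**The case against.** **The rule may not mean this.** A visit that is no longer due is arguably not missed, and SAP 12.1 keeps data up to re-treatment, which points towards retaining the positive biopsy. For an in-field failure treated elsewhere, protocol 4.6.16 says only that later data are excluded; the exit comes from the SAP. The deviation guidance in SAP 12.5 is not among the documents and may already settle the matter. All of this is fair. It makes the literal reading one of two possible readings, but 8.8 as written does not choose between them.

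**Little depends on PP.** No decision rule uses it. ITT counts these men as failures, and the second sensitivity analysis in SAP 12.7.10 expressly keeps men with an early positive in-field biopsy. This stands and limits the point to a supportive analysis. (SAP 12.0 words the denominator as subjects still in the study at 12 months, which sits badly with SAP 12.7.1. That is a separate matter and is not relied on here.)

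**A stronger reading of the therapy item.** A reader might infer that the prior-or-current therapy item also excludes every man given salvage surgery, radiotherapy or hormones on study. The documents do not support that. The item copies exclusion 11, its hormonal sub-item is timed to the procedure, and it sits beside entry conditions such as consent and risk group. HIFU and cryotherapy, which SAP 12.7.8 names as re-treatments, are not in its list. The protocol's footnote on re-treatment, "Note: Exclusion criterion #11 for prior or current prostate cancer therapies does not apply", is needed because eligibility is re-applied at that point; 8.8 does not re-apply it. The remaining defect is that most of the item has no stated time point.

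**A stronger reading of the consequence.** A reader might also infer that PP could rescue a failed trial. The flip at 72/118 depends on the two-sided limit, the band of counts that flip is narrow, and ITT decides the primary hypothesis in any case.

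**Conclusion.** The point holds for the missed-visit item. Applied as written, 8.8 removes from PP a man who is a confirmed early in-field failure and exits for other treatment before the 6-month visit. The direction of the effect is certain: the PP negative-biopsy rate can only rise. Its size rests on an unknown count. At the planned success rate it is about 2 to 4 points for 4 to 6 such men, assuming no other exclusions.

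The conclusion also assumes that visits after a directed exit are treated as missed, which the documents leave undefined, and that the unseen deviation guidance does not say otherwise. The primary ITT analysis is unaffected by 8.8. The therapy item is an ambiguity to tidy. The change is worth making before database lock because it costs almost nothing and removes a judgement that could otherwise be made with outcomes known.

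**What to change.** In protocol 8.8 and in the deviation guidance that SAP 12.5 applies:

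1. Count a follow-up visit as missed only if it was due before study exit or re-treatment.
2. State that any subject with a positive in-field biopsy stays in PP as a failure, unless he has an unrelated major deviation that existed before the failure.
3. As a clarification, tie the therapy item to therapy received before the first NanoKnife procedure.

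The cost is three sentences, with no new data, visits or analyses. The PP rate may come out slightly lower than under the literal reading.
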